5.3 Exclusion criteria

- 1. No written informed consent by individual/parents and/or caregiver.
- 2. Below age 6 and 15 kg weight
- Presence of major systemic illnesses, *e.g.* severe anemia (below 80 g/l Hb according to WHO [28]), clinical malaria as assessed by a medical doctor (positive *Plasmodium* RDT and ≥38 °C ear temperature), upon initial clinical assessment.
- 4. History of acute or severe chronic disease (*e.g.* cancer, diabetes, chronic heart, liver or renal disease).
- 5. Recent use of anthelmintic drug (within past 4 weeks).
- 6. Attending other clinical trials during the study.
- 7. Negative or low egg count (less than 100 EPG or less than 2 out of 4 slides positive) diagnostic result for *T. trichiura* eggs in the stool.
- 8. Known allergy to study medications (*i.e.* albendazole and ivermectin).
- 9. Pregnancy or lactating in the 1st week after birth (according to WHO guidelines within LF control programs [29]).
- 10. Currently taking medication with known interaction (*e.g.* for albendazole: cimetidine, praziquantel and dexamethasone; for ivermectin: warfarin).

5.4 Criteria for discontinuation of trial

A subject can be discontinued from the study for the following reasons:

1. Withdraws from the study (this can happen anytime as participation is voluntary and there are no further obligations once a participant withdraws).

2. At the discretion of the Principal Investigator (PI) or co-PI, if the participant is not compliant to the requirements of the protocol.

```
Page 150 of 176
```

Discontinued subjects will not be replaced. If, for any reason, a subject is discontinued from the study before the end of treatment evaluations, the safety procedures planned (adverse events (AEs) monitoring) will be conducted.

5.5 Treatment of subjects

All *T. trichiura*-infected, consenting, and participating community members will be treated with the respective single or combination treatment regimen at day 0. 400 mg albendazole will be the product of Glaxo Smith Kline (Zentel®) and a single tablet administered. 3 mg tablets of ivermectin (Stromectol®) will be obtained from Merck, France, the weight recorded for each participant and the correct dose evaluated and administered. Matching ivermectin placebo tablets (in terms of appearance) will be produced and a certificate of manufacture and analysis be provided by the University of Basel. To ensure double-blinding the tablets will be repacked into neutral separate plastic bags each containing one albendazole tablet and the maximum number of ivermectin tablets with regard to weight and dose or the corresponding number of placebo tablets. Since albendazole and ivermectin are known to be better absorbed in humans after a high-fat meal was consumed, participants will receive a local high-fat breakfast (sandwich with *e.g.* oily sardines) prior to treatment [30, 31].

All drugs will be administered in the presence of the investigator(s), and ingestion confirmed. This will be recorded with the time and date of closing. Subjects will be asked not to take any drugs other than those prescribed by the study medical team. After ingestion of the medication, the subjects will be observed for 3 hours to ensure retention of the drug. Vomiting within 1-hour post-dosing will require re-dosing. The subjects will not be allowed more than one repeated dose. No re-administration will be needed for subjects vomiting after one hour. The Principal Investigator is responsible for drug accountability at the study site. Maintaining drug accountability includes careful and systematic study drug storage, handling, dispensing and documentation of administration.

Antimalarial treatment (*i.e.*, artemisinin-based combination therapy) will be provided to participants found with clinical malaria (*i.e.* positive *Plasmodium* RDT and \geq 38 °C ear temperature) or severely anemic in combination with a positive RDT result. Iron supplementation will be offered to severely anemic individuals with a negative RDT result.

To avoid interference of potential on-going control programs against helminthiases with the infection status of the trial participants, communication with local stakeholders will be established to ascertain that trial participants will not undergo MDA treatment. Missed-out rounds of planned MDA against helminthiases in study participants will be substituted with a free single-dose treatment (*i.e.* albendazole 400 mg + ivermectin 200 μ g/kg) against STH as well as *S. stercoralis* infection at the study endpoint (after the day 360 follow-up assessment) offered by the study team. At each follow-up time point, participants will be interviewed whether they had taken anthelmintic treatment (e.g. self-purchased, obtained from clinics etc).

5.6 Concomitant therapy

All medications taken one month before and during the study period until the last stool examination must be recorded with indication, dose regimen, date and time of administration.

Medication(s)/treatment(s) permitted during the trial:

- Analgesics and antipyretics are allowed to be given to the subjects in case of fever, antiemetics to prevent nausea and vomiting and/or antibiotics to prevent or treat bacterial superinfection.

Page 151 of 176

Medication(s)/treatment(s) NOT permitted during the trial:

- No other active drugs against helminths are permitted during the trial.

- No drugs with known interactions with the study medication are permitted during the trial.

6. Safety assessments

Few AEs have been reported following ivermectin-albendazole co-administration in STH-infected individuals. The most common AEs were abdominal cramps, headache, fatigue, nausea, diarrhea, fever and vertigo [7, 8, 32]. The safety profile of co-administered ivermectin and albendazole will be assessed through the recording, reporting and analysis of baseline medical conditions, AEs and a physical and clinical examination.

6.1 Adverse event definitions

The term "adverse event" could include any of the following events which develop or increase in severity during the course of the study, after administration of the study product:

a) Any unfavorable and unintended signs, symptoms or disease temporally associated with the use of a medicinal product, whether or not considered related to the condition under study and the study product;

b) Any abnormality detected during physical examination.

The medical conditions present at the initial trial visit that do not worsen in severity or frequency during the trial will not be defined as AEs but be considered baseline medical conditions. For the purpose of this trial, disease progression and relapse will be considered as treatment failure, not as an AE.

The observation time for AEs starts when the treatment is initiated until day 21 (3 weeks after last drug administration).

These data will be recorded on the appropriate case report form (CRF) sections, regardless of whether they are thought to be associated with the study or the drug under investigation. Associated with the use of the drug means that there is a reasonable possibility that the event may have been caused by the drug (see also relatedness definitions below).

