	follow-up prevalence will be determined 14-21 days, 6 months and 12 months post-treatment by collecting another two stool samples. Subjective treatment satisfaction will be assessed 3 hours, 3 weeks and 6 months after treatment to investigate relationship with treatment compliance and observed efficacy in reducing egg output and morbidity.
	All stool samples will be examined with duplicated Kato-Katz thick smears for T. trichiura , A. lumbricoides and hookworm. S. stercoralis infections will be identified using the Baermann technique and recorded qualitatively as larvae-positive or negative. Complementary to stool-based diagnostics, a small portion of urine from each participant will be fixed, transferred to a laboratory at Khon Kaen University in Thailand and examined for antibodies of S. stercoralis using a newly developed ELISA-based assay. For subsequent PCR and microbiome analysis of the stool samples a portion of 1.5-2 g from each specimen will be frozen and preserved in 70% ethanol, respectively and shipped to a reference laboratory at Swiss TPH in Switzerland. At baseline and in the first follow-up (3 weeks post treatment) an additional portion of stool (1.5-2 g) from a subsample of 10 participants identified with heavy intensity infections in each case and study setting will be preserved in 95% ethanol, shipped to the same reference laboratory and subjected to deep sequencing for characterization of T. trichiura strains and investigation of potential resistance markers. Fecal occult blood and calprotectin in stool as markers for gut morbidity and inflammation will be detected using a rapid diagnostic test and an immunoassay, respectively. A subsample of 30 participants will be asked to provide a daily stool sample for a period of up to 4 weeks to monitor dynamics of T. trichiura egg output for subsequent determination of the optimal timing for drug efficacy assessment. Individuals found T. trichiura positive 6 months after baseline will receive a second round of treatment according to their group scheme.

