4.3 Trial design

4.3.1 Baseline survey and screening

A randomized-controlled trial will be conducted with two treatment arms to be followed-up over a 12 months period with an intermediate re-treatment of participants found re-infected after 6 months (Figure). This parallel group trial will be conducted as a multi-country study; thus, in each setting a separate trial according to the design described below will be set up, to provide a better basis for the subsequent generalization of its findings. This arises from the possibility of recruiting the subjects from a wider population and of administering the medication in a broader range of clinical settings, thus presenting an experimental situation that is more typical of future use. The study includes one baseline and three follow-up assessments at 3 weeks (day 21), 6 months (day 180), and 12 months (day 360).
Page 145 of 176

Figure 2. Design and timeline of the randomized-controlled trial to be implemented in each of three settings.

The study is designed as a two-armed trial including one arm with a single drug administration (arm A; albendazole) and one arm with combined treatment through co-administration of separate tablets (arm B; albendazole and ivermectin).

The trial will be conducted as a multi-country study with two settings in Africa and one in Asia, namely Côte d'Ivoire, Pemba (Zanzibar, Tanzania) and Lao PDR.

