4.6 Schedule of visits

Page 148 of 176

 Table 3. Schedule of visits of parallel group trial.

	Screenin g	Baseli	ne/Tr	eatment/	'Safety	Follow up					
	-21 to -1	to -1 Hours Day									
	days	0		3	24	21	180	185	360		
Diagnosis (stool and urine examination)	Х					Х	Х		Х		
Gut morbidity (stool RDTs)	Х					Х	Х		Х		
Informed consent	Х		ent								
Demographics	Х		eatm								
Medical history		Х	nd tro					ment			
Clinical examination		Х	ion a				Х	treat	Х		
Pregnancy testing		Х	mizat				Х	ve re-			
Hemoglobin measurement		Х	ando				Х	electi	Х		
Plasmodium co-infection		Х	R				Х	Š	Х		
Venous blood examination		Х				Х	Х		Х		
Physical functioning		Х					Х		Х		
Capturing AEs				Х	Х	Х					
Capturing SAE				Х	Х	Х					
Treatment satisfaction				Х		Х	Х				

5. Selection of the trial subjects

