6.1.4 Serious adverse events

According to the ICH "Clinical Safety Data Management: Definitions and standards for expedited Reporting E2A" [33], a serious adverse event (SAE) includes any event (experience) or reaction in any untoward medical occurrence that at any dose:

- 1. results in death;
- 2. is life threatening, meaning, the subject was, in the view of the Investigator, at immediate risk of death from the reaction as it occurred, *i.e.* it does not include a reaction that, had it occurred in a more serious form, might have caused death;
- 3. results in persistent or significant disability/incapacity, *i.e.* the event causes a substantial disruption of a person's ability to conduct normal life functions;
- 4. requires in patient hospitalization or prolongation of existing hospitalization;
- 5. creates a congenital anomaly or birth defect (not relevant for this study);
- 6. is an important medical event, based upon appropriate medical judgment, that may jeopardize the patient or subject or may require medical or surgical intervention to prevent one of the other outcomes defining serious.

A "severe" AE does not necessarily meet the criteria for a "serious" AE. SAEs are reported from consent to 3 weeks post-treatment (Day 21).

SAEs that are still ongoing at the end of the study period will be followed up to determine the final outcome.

Page 153 of 176

The causality of any SAE that occurs after the study period and its possible relatedness to the study treatment or study participation will also be assessed by investigators as described in section 6.1.2.

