6.2 Methods of recording and assessing adverse events

Subjects will be kept for observation for at least 3 hours following treatment for any acute AEs. If there is any abnormal finding, the local study physician will perform a full clinical and physical and biochemical examination and findings will be recorded. An emergency kit will be available on site to treat any medical conditions that warrant urgent medical intervention. In addition patients will also be interviewed 3 and 24 hours and again 3 weeks after treatment about the occurrence of AEs (see chapter 4.6).

Information on all AEs (onset, duration, intensity, seriousness and causality) will be immediately entered in the appropriate AE module of the CRF that serves as source document. For all AEs, sufficient information will be pursued and/or obtained so as to permit i) an adequate determination of the seriousness of the event (*i.e.* whether the event should be classified as a SAE); ii) an assessment of the casual relationship between the AE and the study treatments and iii) an assessment of intensity of AEs will be judged by the study physician.

All SAEs or SUSARs must be reported as described in Section 6.3.

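### The AE and SAE windows close at day 21, but participants positive at 6 months get a second allocated dose at about day 185, after which no dated AE/SAE enquiry is scheduled

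*Combined protocol and SAP*

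**What the plan says.** References are to the Laos protocol unless another is named.

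- **AE window (6.1):** "The observation time for AEs starts when the treatment is initiated until day 21 (3 weeks after last drug administration". The Swiss (EKNZ), Pemba and Côte d'Ivoire texts have the same sentence.
- **SAE window (6.1.4):** "SAEs are reported from consent to 3 weeks post-treatment (Day 21" in the Laos, Swiss and Côte d'Ivoire texts. Pemba stops at 24 hours. All four add that the causality of an SAE arising after the study period will also be assessed.
- **Second dose:** section 4.3.1 describes follow-up "with an intermediate re-treatment of participants found re-infected after 6 months". The Synopsis (Measurements & procedures) says that those "positive 6 months after baseline will receive a second round of treatment according to their group scheme". The schedule in 4.6 places selective re-treatment at day 185.
- **Observation after dosing:** section 6.2 says "Subjects will be kept for observation for at least 3 hours following treatment for any acute AEs", and 5.5 says "the subjects will be observed for 3 hours to ensure retention of the drug". Neither is limited to day 0.
- **Interviews (6.2):** "patients will also be interviewed 3 and 24 hours and again 3 weeks after treatment about the occurrence of AEs (see chapter 4.6". The sentence does not say which treatment is meant.
- **Schedule (4.6):** the row "Capturing AEs" and the SAE row below it are marked at 3 hours, 24 hours and day 21. There is no visit between days 185 and 360, and neither row is marked at day 360.
- **AE data list (7.4, item 4; also Swiss and Côte d'Ivoire):** active probing at 3 and 24 hours, then collection at the 3-week follow-up.
- **SAE notification (6.3):** any SAE is notified within 24 hours of becoming known, with no end date.

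**The concern.** The two halves of the 6.1 sentence agree only if each participant is dosed once. The protocol plans a second dose for anyone still or again positive at 6 months, so the fixed day does not fit those participants. The schedule and the AE data list follow the fixed day.

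Safety and tolerability of the regimens is secondary objective a. A non-serious event that begins more than 3 hours after the second dose lies outside the day-21 window and outside any dated enquiry. For serious events, 6.1.4 ends at day 21 while 6.3 is open-ended, so a site cannot tell which rule applies.

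Two other provisions point the same way. Section 10.4 justifies having no data and safety monitoring board partly by single-dose treatment. The Swiss and Côte d'Ivoire texts (4.3.1) repeat the filariasis test at 6 months, before possible re-treatment, and use the results to explain differences in AE reporting; no AE interview is clearly scheduled after re-treatment to supply that comparison.

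**Working it through.** **1. Timing**

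- The stated windows close at day 21, which is 185 − 21 = 164 days before the second dose.
- Three weeks after the second dose is 185 + 21 = day 206.
- The next scheduled visit is 360 − 185 = 175 days after the second dose.
- The day-185 column of the schedule holds only a procedure banner, so its blank AE cell is not used as evidence.

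**2. Reproducing the plan's figures**

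Inputs from 7.2: cure 30% (albendazole) and 50% (combination), same efficacy at re-treatment, 10% reinfection per 6 months, 90% power, two-sided 5%.

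- Sample size with unpooled variance: n = (p₁q₁ + p₂q₂)(1.960 + 1.282)² / d² = (0.21 + 0.25) × 10.507 / 0.20² = 120.8, so 121 per arm. Then 121 / 0.85 = 142.4, so 143. Both match.
- Negative at 6 months: 0.30 × 0.90 = 0.27 and 0.50 × 0.90 = 0.45. Positive: 0.73 and 0.55.
- Negative at 12 months if all positives are re-treated: (0.27 + 0.73 × 0.30) × 0.90 = 0.440 and (0.45 + 0.55 × 0.50) × 0.90 = 0.6525. The plan states 44% and 65%.
- The same formula at the unrounded rates gives 110.2, so 111 per arm, as stated.

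Section 4.3.1 speaks of re-infected participants. Re-treating only those cured and then re-infected would give (0.27 + 0.03 × 0.30) × 0.90 = 0.251 and (0.45 + 0.05 × 0.50) × 0.90 = 0.428, which do not match. The plan's figures therefore imply that all 6-month positives are re-treated, as the Synopsis says.

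**3. Second doses without a dated enquiry, per country**

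| Case | Seen at 6 months, per arm | Second doses | Share of administrations |
|---|---|---|---|
| 300 per arm, 30% loss (7.2) | 210 | 210 × 0.73 + 210 × 0.55 = 153.3 + 115.5 = 268.8 | 268.8 / (600 + 268.8) = 30.9% |
| 300 per arm, no loss | 300 | 300 × 1.28 = 384 | 384 / (600 + 384) = 39.0% |
| 143 per arm (SAP), 30% loss | 100.1 | 100.1 × 1.28 = 128.1 | 128.1 / (286 + 128.1) = 30.9% |

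The third row combines two sources: 143 was inflated for 15% loss, the SAP gives no 6-month loss, and the 30% is borrowed from the 300-per-arm rationale.

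Female participants are pregnancy-tested at day 180, so some positives may not be re-dosed; the documents give no figure. Assuming 10% are not, the first row becomes 268.8 × 0.90 = 241.9 and 241.9 / 841.9 = 28.7%.

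**The case against.** The best defence is that the text is ambiguous rather than silent. The parenthesis in 6.1 ties the window to the last administration, which already gives about day 206 for a re-treated participant. The 6.2 interviews follow treatment without naming day 0. On that reading only the day label is out of date. This stands in part: the text is internally inconsistent, not plainly without provision. But 6.2 sends its interviews to chapter 4.6, and both 4.6 and item 4 of 7.4 list AE capture only at 3 hours, 24 hours and the 3-week follow-up. Whichever half of the sentence prevails, it needs correcting.

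A reader might infer that serious events after the second dose would go unreported. The documents do not support that: 6.3 has no end date, and 6.1.4 provides for causality assessment of SAEs after the study period. What is missing is a prompted question and a consistent window. Nor is the second dose wholly unobserved, since the 3-hour observation and AE recording are not limited to day 0. Records of concomitant medication with its indication (5.6) and the day-360 examination may leave traces, but neither is an AE enquiry.

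It is also fair to say that these are widely used drugs, that the second dose repeats a regimen already taken, and that active enquiry is best placed after the fully randomised first dose. That limits the seriousness of the gap. It does not justify a window that contradicts itself.

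**Conclusion.** The point holds as an inconsistency in the safety rules and a gap in scheduled collection. For participants re-dosed at about day 185, the day-21 limit in 6.1 and 6.1.4 is wrong as written, and no dated AE/SAE enquiry is scheduled after that dose.

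The planning size is about 269 second doses per country at 300 per arm with 30% loss (31% of administrations), 384 (39%) with no loss, and about 128 at 143 per arm with 30% loss. These rest on the protocol's cure and reinfection assumptions and on re-treatment of all 6-month positives. They should not be read as upper limits, because they move with the 6-month loss and with the number actually re-dosed. They count doses; nothing here estimates missed events or suggests that the second dose is unsafe.

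A reader might also infer that the trial's main results are compromised. They are not: the primary endpoint is read at 14–21 days, and the SAP covers the 3-week data and marks days 180, 185 and 360 as outside its scope.

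The printed Côte d'Ivoire text is dated 12.06.2018 and still contains the dose-finding study, whereas the SAP cites a version of 22.11.2018. The operative wording there should be checked. The correction is worth making because it is cheap and bears on a stated secondary objective.

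**What to change.** - In 6.1 and 6.1.4 of each operative country protocol, define the AE/SAE window as three weeks after each study drug administration: day 21, and about day 206 if re-treated.
- Make 6.3 consistent with that window while keeping later SAEs notifiable.
- In 6.2, state which dose the 3-hour, 24-hour and 3-week interviews follow.
- In 4.6, mark AE/SAE capture at the day-185 dosing contact, using the existing 3-hour observation, and add one question on serious or notable events at day 360.
- Report second-dose events separately by arm and descriptively, because re-treated participants are selected by their 6-month result.
- As a separate correction, align Pemba's 24-hour SAE clause with the day-21 SAE capture in its own schedule.

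The cost is a wording amendment and a few case report form lines at existing contacts, with no new visits. The limitation is real: without a 24-hour or 3-week interview after the second dose, mild events starting more than 3 hours after it remain largely uncaptured, and a question asked 175 days later will mainly find serious or memorable ones. The gain is a correct window and a record of acute and serious second-dose events.

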6.1.1 Severity grading

Adverse signs or symptoms will be graded by the Investigator as mild, moderate, severe or life threatening according to the following definitions:

Grade	Definition
1	Mild : the subject is aware of the event or symptom, but the event or symptom is easily tolerated.
2	Moderate : the subject experiences sufficient discomfort to interfere with or reduce his or her usual level of activity.
3	Severe: significant impairment of functioning: the subject is unable to carry out his or her usual activities.
4	Life threatening or disabling

Page 152 of 176

5 Death related to adverse events

